1. BACKGROUND

1.1. PERIPHERAL ARTERIAL DISEASE

The term “peripheral arterial disease” (PAD) is widely used to refer to atherosclerotic disease that obstructs the blood supply to the lower limbs. The clinical manifestations of PAD are a major cause of acute and chronic illness. Patients with PAD experience progressive decrements in functional capacity and quality of life. PAD frequently coexists with coronary and / or cerebrovascular disease, likely due to a similar underlying pathology and shared risk factors (e.g., smoking, hyperlipidemia, hypertension, and diabetes). Patients with PAD have a 20% - 60% increased risk for myocardial infarction (MI), a two- to six-fold increased risk of cardiovascular death, and a 40% increased risk of stroke.^{1,2} This higher level of morbidity and mortality occurs, in part, because many affected patients are asymptomatic and remain undiagnosed for years, allowing the disease to progress unchecked. Clinical symptoms often only manifest when the disease state is advanced.³

It is estimated that PAD now affects 8 to 12 million people in the United States. The prevalence of symptomatic PAD increases with age and with number of risk factors. PAD occurs in 1% - 4% of the population over the age of 40, and is reported to be as high as 30% in patients over 70 or in patients older than 50 years with a history of diabetes, smoking, or both.⁴⁻⁶ As the population ages, this number will increase.

1.2. CRITICAL LIMB ISCHEMIA

Critical limb ischemia (CLI) is the end-stage manifestation of PAD. One to three percent of newly diagnosed PAD patients initially present with CLI; 5%-10% of all other PAD patients eventually progress to CLI. The natural history of CLI has been well documented to have an inexorable downhill course. CLI patients experience ischemic rest pain (Rutherford category 4), ischemic skin lesions, and ulcers or gangrene (Rutherford category 5-6). Amputation of the affected limb remains a common procedure and is likely to occur more frequently due to an aging population.⁷ The incidence of major amputations ranges from 120 to 500/million/year.⁶ In patients with the comorbidities of diabetes mellitus or renal insufficiency, the rate of amputation can be much greater.^{7,8}

1.3. TREATMENT OPTIONS FOR CLI

The primary treatment goals in patients with CLI are to relieve ischemic pain, heal (neuro) ischemic ulcers, prevent limb loss, improve patient function and quality of life and prolong overall survival. Therefore, reestablishing blood supply to the affected limb, when possible, is critical. In addition to successful revascularization, the institution of lifestyle changes, atherosclerotic risk factor modification, and pharmacologic therapies are also used to reduce cardiovascular morbidity and mortality. Narcotic medications are often used for analgesia and for assistance with sleeping.

1.3.1. REVASCULARIZATION OPTIONS

Revascularization options for patients with CLI range from open surgical procedures (bypass grafts) to various endovascular procedures. The treatment approach depends on a careful evaluation of a patient's current medical condition (comorbidities), the location and extent of the lesion, and the availability of an autologous conduit (e.g. saphenous vein).⁹⁻¹¹ Although arterial bypass surgery has long been considered the preferred first line treatment modality, many of the newer endovascular technologies can be used with similar success rates and with reduced morbidity.^{12,13}

Percutaneous transluminal angioplasty (PTA) has been shown to be effective, with limb salvage rates comparable to surgical procedures. Stents placement is usually attempted after failed PTA. Adjunctive therapies such as lasers, thermal angioplasty and atherectomy devices have not yet demonstrated improved efficacy when compared with conventional lower extremity interventions.^{14,15}

1.3.2. AMPUTATION

Amputation is considered when revascularization is not feasible due to the location and extent of atherosclerosis, when a patient is unable to tolerate a procedure, or when a patient is unlikely to have a functional extremity despite restoration of distal flow (e.g. due to dementia, chronic illness, etc.). While amputation does eliminate the source of pain at rest and all necrotic tissue,¹¹ it is associated with a significantly elevated perioperative and one year mortality rate.^{1,6,16}

1.3.3. UNMET CLINICAL NEED

In the absence of revascularization options, most patients with CLI require amputation within 6 months. Patients requiring major amputation face a diminished quality of life, an unfavorable natural history and need extensive resources for their post-amputation rehabilitation and course. The 1-year amputation-free survival rate for patients diagnosed with CLI is 45%; the mortality rate is approximately 25% and may be as high as 45% in those who have undergone amputation.^{1,6,16} Management of this end-stage disease process consumes a significant amount of healthcare resources.^{17,18} Clearly, new therapeutic approaches are required.

1.4. THERAPEUTIC ANGIOGENESIS IN ISCHEMIC LIMB DISEASE

Two key processes determine the amount of blood flow to skeletal muscle in patients with CLI: 1) the degree of arterial occlusion, and 2) the degree to which an endogenous angiogenic response is mounted to compensate for the occlusion. Ischemic tissue injury causes the release of numerous mediators, including growth factors, transcription factors, and signaling molecules known to stimulate angiogenesis and growth of collateral vessels.^{19,20} However, this physiologic response to pathophysiologic processes is often inadequate to prevent clinical manifestations of ischemia.

A growing area of research has focused on elucidating the molecular mechanisms underlying angiogenesis. The goal is to identify and harness the critical molecular players that initiate and / or regulate angiogenic growth. A number of cytokines such as vascular endothelial growth factor (VEGF) and fibroblast growth factor (FGF) have been studied intensively and early phase I/II studies have been conducted. The data thus far have been mixed.²¹⁻²⁶

Hepatocyte growth factor (HGF) has been shown to be a potent angiogenic growth factor stimulating the growth of endothelial cells and migration of vascular smooth muscle cells.^{27,28} It is a multi-functional mesenchyme-derived cytokine with potent angiogenic and anti-apoptotic effects²⁷⁻³⁰ HGF stimulates DNA, RNA and protein synthesis by endothelial cells in a dose -dependent manner and attenuates high D-glucose-induced endothelial cell death. HGF has also been shown to upregulate VEGF expression, and has demonstrated greater mitogenic activity than that of VEGF alone in human aortic endothelial cells *in vitro*.^{31,32} Recently, HGF gene transfer has been shown to produce significant augmentation of collateral formation in rabbit hind limb ischemia model.²⁸ Furthermore, a significant increase in blood flow was achieved by HGF gene transfer both in rat diabetic and non-diabetic hind limb ischemia models.^{30,33}

Because of its pluripotent capabilities, increasing the availability of HGF in ischemic tissues to achieve therapeutic angiogenesis has been a growing area of research. The challenge associated with delivering a targeted sustained dose of exogenous HGF to ischemic tissues is in overcoming the instability of HGF in blood circulation and its rapid clearance by the liver; HGF has an *in vivo* half-life of less than 15 minutes.^{34,35}

One approach to increasing HGF in ischemic tissues is to develop a gene transfer strategy that would allow for persistent expression of HGF protein *in vivo*. Although plasmid DNA is one of the least efficient gene transfer systems currently in use, the fact that it is associated with limited persistence and no propensity for genomic integration, (particularly in skeletal muscle tissue) makes it an attractive option for local targeted delivery in ischemic tissues.

1.5. VM202

The investigational agent being studied in this protocol is VM202. VM202 is a DNA plasmid that contains novel genomic cDNA hybrid human hepatocyte growth factor (HGF) coding sequence (HGF-X7) expressing two isoforms of HGF, HGF₇₂₈ and HGF₇₂₃.

The key feature of HGF-X7 is that it was designed by inserting a series of intron sequences into certain sites of HGF cDNA so that both isoforms of HGF protein are expressed simultaneously and efficiently as in the human genome. Because there is no change in the coding region of the HGF gene, HGF proteins generated from VM202 are identical to the wild-type human HGF proteins. VM202 has been developed using the pCK DNA plasmid that has been safely used in previous

ViroMed-sponsored human clinical trials with VEGF₁₆₅ as the therapeutic gene, known as VM202.

[figure not shown]

Figure 1. VM202 construct

Safety of VM202. The use of plasmids for targeted delivery of angiogenic factors into muscle tissue is a particularly attractive and a relatively safe therapeutic approach, because plasmids have been shown to effectively transfect postmitotic cells such as skeletal and heart muscle and to successfully express angiogenic genes with very little dissemination and persistence at distant sites. Following intramuscular injection, the plasmid that persists is extrachromosomal and integration into host DNA, if it occurs, is negligible.³⁶⁻³⁸ This local effect of conventionally injected naked plasmid DNA is well known.^{39, 40}

Potential Efficacy of VM202. VM202 has demonstrated potential for stimulating angiogenesis in animal models. The development of new blood vessels may improve blood flow to peripheral nerves and potentially replace damaged capillary bed. VM202 may have the ability to increase perfusion and wound healing, as well as decrease pain due to neuropathy brought on by ischemia.

1.6. PRECLINICAL DATA

The non-clinical safety of VM202 has been evaluated for general toxicity following single intramuscular and intravenous doses in rats. In addition, the general toxicity of VM202 following multiple intermittent (weekly or monthly) intramuscular doses has been evaluated in rabbits and rats, respectively. The potential for genomic integration at the injection site as well as the potential for distribution to and persistence of VM202 in reproductive tissues was evaluated in rats. The ability of VM202 to induce humoral immune responses was evaluated following intramuscular administration with or without adjuvant in mice. All species utilized for these studies (mouse, rat, and rabbit) were shown in *in vivo* experiments to be able to express the plasmid following intramuscular injection.

An ischemic heart disease efficacy study in a Yorkshire swine model demonstrated that intramyocardial administration of VM202 increased the capillary density and regional perfusion in ischemic myocardium and improved ischemic left ventricular function. An ischemic heart disease efficacy study in rats demonstrated that

histologically identifiable capillaries increased following intramuscular administration of VM202 (versus pCK and pCK-VEGF₁₆₅; $p < 0.001$).

Collectively, VM202 has been well-tolerated in all studies conducted to date, with the only evidence of toxicity consisting of mild, transient injection site irritation in rats at a dose level 6-fold above the human clinical dose of 16 mg (0.23 mg/kg for a 70 kg patient), the maximum dose administered on a single day in the phase I study. There has been no evidence of systemic toxicity in any study and human HGF has not been detected in the sera of rats or rabbits following intramuscular injection [lower limit of quantitation (LLOQ) = 125 pg/mL]. There is no evidence of genomic integration, potential germ cell transmission, or immunostimulatory effects following intramuscular administration of VM202 to animals.

Therefore, the nonclinical efficacy and safety studies support the continued clinical investigation of VM202 in patients with critical limb ischemia.

Preliminary Conclusions. These early data support the feasibility of intramuscular injections of VM202 in subjects with critical limb ischemia. They suggest that this therapeutic approach may improve functional outcomes and provide symptomatic relief. VM202 is rapidly eliminated from circulation, and appears to remain active only at the injection site. The incidence of complications, while high, did not appear to be significantly different between treatment cohorts. Continued study of VM202 in patients with CLI and / or diabetes is warranted.

1.8. STUDY AND DOSE RATIONALE

Based on the promising results seen in the phase I study, two doses (8 mg and 16 mg final VM202 dose) will be tested and compared to placebo injections in this phase II study. Patients will be treated with a final dose of 8 mg VM202, 16 mg VM202 or placebo by intramuscular injections in the affected calf on Day 0, Day 14, Day 28 and Day 42. VM202 will be delivered in a solution of 0.5 mg VM202 / mL.

As there are currently no approved drugs that can reverse CLI and as most patients have exhausted surgical and endovascular intervention options, inducing angiogenesis in the affected limb with VM202 may result in an increase in tissue perfusion, which, in turn improve wound healing, reduce pain and improve limb salvage rates.

2. GOOD CLINICAL PRACTICES STATEMENT

This trial will be conducted in compliance with all applicable federal regulations pertaining to investigational drugs and devices including but not limited to: 21 CFR Part 50, Part 54, Part 56, Part 312, and Good Clinical Practice standards. This trial will be conducted in compliance with the protocol as approved by an Institutional Review Board (IRB) and an Institutional Biosafety Committee (IBC). Any deviations from the protocol will be immediately reported to the Sponsor and to the IRB and IBC per each institution's guidelines.

3. INVESTIGATIONAL PLAN

3.1. STUDY OBJECTIVES

The objective of this Phase II study is to evaluate the safety of IM administration of VM202 in subjects with moderate or high-risk CLI (Rutherford Clinical Severity Score equal to 4 or 5) who are poor or non- candidates for surgical or percutaneous revascularization; and, to evaluate potential bioactivity of IM administration of VM202 in subjects with CLI, when compared with placebo, on rest pain (as assessed by frequency of rest pain, pain medication use history, sleeping history, and intensity of rest pain) or leg ulcer healing (as assessed by ulcer surface area, time to complete healing), perfusion (MRA), hemodynamic assessment (ABI & TBI), tissue oxygenation (TcPO₂) and the incidence and extent of lower leg amputation or other surgical interventions.

3.2. STUDY DESIGN

This is a 12 month phase II, double-blind, randomized, placebo-controlled, multicenter study designed to assess the safety and efficacy of VM202 in subjects with critical limb ischemia. Patients with critical limb ischemia will be screened for study eligibility after giving informed consent. Screening will include assessment of study eligibility, a complete medical history, physical exam, cancer screening tests, viral screening, ABI & TBI, TcPO₂, VAS, 12 lead EKG, retinal fundoscopy, clinical chemistry, hematology, urinalysis, and pregnancy test (women of childbearing potential only), and documentation of any ulcers or gangrenous areas. With the exception of ulcer measurement, VAS, ABI & TBI and TcPO₂ which will be repeated prior to first injection, procedures conducted during screening will represent the baseline reference values. Screening/Baseline assessments should occur within the 60 days prior to Day 0 (day of injection).

Patients who meet the eligibility criteria will be randomly assigned in a 2:2:1 fashion to one of the three treatment arms: Low Dose (8 mg VM202), High Dose (16 mg VM202), or placebo, respectively. Assignment to a treatment arm will be centralized, using an independent predetermined randomization scheme in a double-blinded fashion. Blinding will be achieved by having the study medication (test and control products) prepared by the study pharmacist. Reconstituted VM202 is indistinguishable from saline solution.

Prior to the first injection, vital signs, concomitant medications, serum chemistry and hematology, ulcer evaluation, VAS, ABI & TBI, TcPO₂, VascuQol, serum HGF, and copies of VM202 will be determined. MRA will also be conducted as a sub-study at up to two sites.

Patients will receive VM202 or placebo (normal saline) by intramuscular injections in the calf chosen for treatment on Day 0, Day 14, Day 28 and Day 42. VM202 will be delivered in a solution of 0.5 mg VM202 / mL. Study drug will only be administered unilaterally.

Patients in the Low Dose Group (8 mg VM202) will receive:

- Day 0: 4 mg of VM202 (16 injections of 0.5 ml of VM202)
- Day 14: 4 mg of VM202 (16 injections of 0.5 ml of VM202)
- Day 28: Placebo only (16 injection of 0.5 ml normal saline)
- Day 42: Placebo only (16 injection of 0.5 ml normal saline)

Patients in the High Dose Group (16 mg VM202) will receive:

- Day 0: 4 mg of VM202 (16 injections of 0.5 ml of VM202)
- Day 14: 4 mg of VM202 (16 injections of 0.5 ml of VM202)
- Day 28: 4 mg of VM202 (16 injections of 0.5 ml of VM202)
- Day 42: 4 mg of VM202 (16 injections of 0.5 ml of VM202)

Patients in the placebo control group will receive 16 injections of 0.5 ml normal saline at each visit.

Table 1 lists the final dose and dose per visit to be administered by study arm.

Table 1. VM202 administration for each study arm

TREATMENT GROUP	FINAL DOSE VM202	DOSE VM202 (MG) PER VISIT			
		DAY 0	DAY 14	DAY 28	DAY 42
Low Dose	8 mg	4	4	0	0
High Dose	16 mg	4	4	4	4
Placebo	0	0	0	0	0

Determination of HGF serum levels will be made immediately pre-treatment on Day 0, immediately pre-treatment on Day 42, Day 49 and Day 90. The number of copies of VM202 in whole blood will be determined at Day 0 (pre-injection, and 2 hours post injection), Day 42 (pre-injection, and 2 hours post injection), Day 49, Day 90, and at 6 months. VAS assessment will be performed at Day 0 (pre-injection), Day 14 (pre-injection), Day 28 (pre-injection), Day 42(pre-injection), Day 90, at 6 months, 9 months, and 12 months. VascuQol will be administered on Day 0 (pre-injection), Day 90, at 9 months, and 12 months. ABI & TBI will be recorded at Day 0 (pre-injection), Day 28 (pre-injection), Day 90, at 6 months, 9 months, and 12 months. TcPO₂ will be measured at Day 0 (pre-injection), 6 months, 9 months, and 12 months. Ulcer measurements will be performed at Day 0, Day 14, Day 28, Day 42, Day 49, Day 90, at 6 months, 9 months, and 12 months. MRA will be conducted as a sub-study at up to two sites on Day 0 (pre-injection) and at 6 and 9 months. Retinal funduscopy will be conducted at 12 months. Adverse events will be recorded throughout the one year follow-up period.

A summary of the schedule of evaluations and visits from screening through the end of the study can be found in Appendix 1.

3.3. PATIENT POPULATION

Fifty (50) patients meeting the following study entry criteria will be enrolled.

3.3.1. INCLUSION CRITERIA

1. Male or female, between 18 and 90 years of age;
2. Diagnosis of critical limb ischemia (Rutherford Class 4 or 5), including:
 - A resting ankle systolic pressure (in either the dorsalis pedis or posterior tibial arteries) of ≤ 70 mmHg in the affected limb; or
 - A resting toe systolic pressure of ≤ 50 mmHg in the affected limb; or
 - For patients in which measurement of ankle systolic pressure is not feasible (e.g. vessel calcification and non-compressibility), $TcPO_2 \leq 30$ mmHg;
3. Poor or suboptimal candidate for bypass graft surgery or percutaneous angioplasty;
4. Pain at rest, and/or ischemic ulcers, and/or focal gangrene (< 3 cm²) for a minimum of 2 weeks;
5. Significant stenosis ($\geq 75\%$) of one or more of the following arteries: superficial femoral, popliteal, or two or more infra-popliteal arteries as verified by angiography within 12 months prior to enrollment;
6. Be willing to maintain current drug therapy for peripheral arterial disease throughout the course of the study including an anti-platelet, hypertension and statin treatment unless not tolerated;
7. Clinically stable on optimized medical regimen for ≥ 30 days;
8. Be capable of understanding and complying with the protocol and signing the informed consent document prior to being subjected to any study related procedures;
9. Women who are surgically sterile or at least 1 year postmenopausal or who have been practicing adequate contraception for at least 12 weeks prior to entering the study. If the subject is of child-bearing potential, she must have a negative urine pregnancy test result prior to study enrollment and must agree to repeat pregnancy screening tests during the study. If the subject or the subject's partner(s) is of child bearing potential, the subject and the subject's partner(s) must agree to use a "double barrier" method of birth control while participating in this study.

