3.4.3. SCREENING (DAY -60 TO DAY 0)

Patient enrollment is subject to the rules established in Section 3.2 for randomization, but screening procedures can proceed provided the Investigator waits for enrollment confirmation from ViroMed or its Designee.

The following procedures / evaluations will be conducted at screening:

- Obtain informed consent prior to any study-related procedures
- Evaluation of eligibility
- Complete Medical History
- Vital Signs
- Complete Physical Exam
- Concomitant Medications
- Cancer screening – including cancer markers (carcinoembryonic antigen (CEA), alpha fetoprotein (AFP), CA19-9, and CA125 (females only)); pap smear and mammogram if not performed within past 12 months (females only); chest X-ray or CT scan of the chest (if the patient has a previous history of tobacco use, a CT scan will be performed instead of the chest X-ray) within 3 months prior to study entry; PSA (males only); for patients ≥ 50 years old, colonoscopy within past 10 years
- Retinal Fundoscopy - fluorescein angiography may be conducted in cases where funduscopy alone is deemed insufficient
- Viral screening – HIV, Anti-Human T-Cell Lymphotropic Virus (HTLV)

-
- Positive Hepatitis B or C as determined by Hepatitis B core antibody (HBcAB), antibody to Hepatitis B antigen (IgG and IgM; HbsAB), Hepatitis B surface antigen (HBsAg) and Hepatitis C antibodies (Anti-HCV), at Screening
 - Serum chemistry and hematology
 - Urinalysis
 - Urine pregnancy test (for women of childbearing potential only)
 - Photograph and measurement of ulcer(s) – if present
 - ECG
 - Visual Analog Scale (VAS) score
 - ABI & TBI
 - TcPO₂

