3.4.6. DAY 0 – 1ST INJECTIONS

3.4.6.1. PRE-INJECTION (WITHIN 4 HRS PRIOR TO INJECTIONS)

- Concomitant Medications
- Vital Signs
- Serum Chemistry and hematology
- Serum HGF
- Copies of VM202 in whole blood
- Visual Analog Scale (VAS) score
- VascuQol
- ABI & TBI
- TcPO₂
- Photograph and measurement of ulcer(s) – if present
- MRA – sub-study to be only at designated site(s) –to be completed within 7 days prior to Day 0

3.4.6.2. 1ST DOSE OF VM202 / PLACEBO

- Intramuscular injections of VM202 in calf (unilateral)

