3.5.2. DISCONTINUED PATIENTS

Any patient may voluntarily discontinue the study at any time without prejudice. The investigator may discontinue a patient from the study at any time if (s)he considers that remaining in the study compromises the patient's health or the patient is not sufficiently cooperative. In either event, reason(s) for discontinuation should be recorded on the CRF.

Possible reasons for study discontinuation include the following:

- AEs necessitating discontinuation from the study (pre-treatment).
- The patient is lost to follow-up.
- Patient decision (specify).
- Investigator decision (specify).
- Other reason (specify).

The reasons for any patient discontinuation will be recorded on the study completion form of the CRF.

Discontinued patient(s) will be replaced in any treatment arm if discontinuation occurs prior to the 90 Day follow-up;

Patients discontinued for AE(s) will be followed-up after patient's discontinuation until the event is resolved or considered medically stable by the investigator.

Subjects that withdraw prior to study completion will undergo the following if possible:

- Retinal Fundoscopy
- Concomitant Medications
- Serum Chemistry and hematology
- Photograph and measurement of ulcer(s) if present at baseline
- Vital Signs
- Serum HGF if discontinued prior to Day 90
- Copies of VM202 in whole blood if discontinued prior to Day 90
- Injection site reaction assessment if discontinued prior to Day 49
- Adverse Events

In case of a patient lost-to-follow-up, the investigator must do his/her best to contact the patient (by phone or letter) at least twice. If no response is obtained from the patient, the investigator is encouraged to contact one of the patient's relatives or his/her general practitioner. The evidence of these contacts must be recorded in the patient medical chart. It can be, for instance, the acknowledgement of receipt of a letter sent to the patient.

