4. EXAMINATIONS AND EVALUATIONS

4.1. EVALUATIONS CONDUCTED AT BASELINE ONLY

4.1.1. COMPLETE MEDICAL HISTORY

A complete medical history will be obtained at Baseline. All positive and negative findings will be carefully documented on the CRF. Any new finding discovered during the Baseline evaluation and prior to the first study drug administration (Day 0) will be considered to be part of the medical history and will not be recorded as an adverse event.

The Investigator will perform an especially detailed assessment of past peripheral arterial disease history to include all events and interventions for critical limb ischemia and to excluded other (e.g. structural abnormalities such as fibromuscular dysplasia or connective tissue disorders, inflammatory conditions, thromboembolic disease, impingement/entrapment, venous claudication, etc.).

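### Women of child-bearing potential must agree to repeat pregnancy tests, but neither the protocol nor the SAP schedules any test after screening

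*Protocol*

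**What the plan says.** Inclusion 9, in the synopsis and in Protocol 3.3.1, requires a negative urine test before enrollment and adds that the woman "must agree to repeat pregnancy screening tests during the study". It gives no visit and no frequency. The same criterion requires adequate contraception for at least 12 weeks before entry, or sterility or menopause, and a double-barrier method during participation.

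The operational sections are consistent with one another and place the test at screening only:

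- Section 3.4.3 lists the urine test at screening.
- Sections 3.4.6 to 3.4.14 cover Days 0, 14, 28, 42, 49 and 90 and Months 6, 9 and 12. None lists it.
- Section 3.5.2, the early-withdrawal list, omits it.
- Section 4.1.7 places it at screening, under the 4.1 heading "EVALUATIONS CONDUCTED AT BASELINE ONLY".
- Protocol Appendix 1 and SAP Table 2 each tick it once, in the screening column.

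On timing, Protocol 3.2 says "Screening/Baseline assessments should occur within the 60 days prior to Day 0 (day of injection"). Appendix 1 shows the same 60 days, whereas the screening column of SAP Table 2 runs from Day -30.

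**The concern.** The entry criterion foresees repeat testing and the schedule does not provide for it. The visit lists cannot easily be read as partial: 3.4.1 introduces them as the detailed account of the visits and what each requires. Section 3.2 also names the screening assessments to be repeated before the first injection (ulcer measurement, VAS, ABI and TBI, TcPO₂), and the pregnancy test is not among them. A site can therefore comply fully with the schedule and do no repeat test.

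The practical gap is at dosing. A pregnancy that begins after screening meets no scheduled test before any of the four injection visits. There is also a smaller problem of conduct. The SAP's per-protocol population excludes subjects with protocol violations or major deviations. With no visit named, neither a monitor nor the blinded population review can say whether a missing repeat test is a deviation.

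**Working it through.** The plan gives no figure to reproduce. The check is a comparison of sections, followed by simple arithmetic on how old the only scheduled test can be at each injection.

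**Count of scheduled tests.** Screening list: 1. Nine later visit lists: 0. Early-withdrawal list: 0. Appendix 1 and SAP Table 2: one tick each, at screening.

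**Inputs for test age.**
- Screening window W: 60 days (Protocol 3.2, 3.4.3 and Appendix 1) or 30 days (SAP Table 2).
- Injection days: 0, 14, 28 and 42, the last three with a window of ±3 days (Protocol 3.4.7 to 3.4.9).

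**Formula.** Greatest age at Day 0 = W. Greatest age at a later injection on day d = W + d + 3.

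| Injection | W = 60 days | W = 30 days |
|---|---|---|
| 1 (Day 0) | 60 | 30 |
| 2 (Day 14) | 60 + 14 + 3 = 77 | 30 + 14 + 3 = 47 |
| 3 (Day 28) | 60 + 28 + 3 = 91 | 30 + 28 + 3 = 61 |
| 4 (Day 42) | 60 + 42 + 3 = 105 | 30 + 42 + 3 = 75 |

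Injection 4 is the last active dose in the 16 mg arm. In the 8 mg arm the last active dose is injection 2, so the corresponding maximum there is 77 days (47 under the SAP column).

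**Shortest possible gap.** If the screening test were taken on Day 0 itself (W = 0), it could still be 42 + 3 = 45 days old at injection 4. Screening and dosing on one day is in any case unlikely, because 3.4.4 and 3.4.5 put treatment authorization and shipment of the kit between them.

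**Number of women.** The documents give none. Protocol 1.1 notes that "The prevalence of symptomatic PAD increases with age and with number of risk factors", and postmenopausal and surgically sterile women are eligible, so the subgroup may be empty. Entry is nevertheless open from age 18 and expressly provides for women of child-bearing potential.

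**The case against.** The strongest reply is that the risk is already controlled and the group is tiny. Contraception is required before and during the study, 4.1.7 asks for it to be documented, and there may be no such woman among the 50 subjects. That stands as a limit on the size of the problem. It does not remove it, since inclusion 9 asks for contraception and repeat tests together.

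A second reply is that the criterion obliges the woman only to agree to tests, which could mean testing as needed. That reading is possible but less natural. It also leaves sites without any statement of when a test is needed.

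A third is that the timing may be given elsewhere. The sample consent form (Appendix 2) is not in the text reviewed, and the Study Manual was not available. Either might name visits, but Appendix 1 and the visit lists would still lack them. SAP Listing 10 has a visit column for the urine test; a listing layout schedules nothing.

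A reader might infer more than the documents support in two directions. One inference is that the plan exposes women to a known fetal hazard. Protocol 1.6 reports no evidence of genomic integration, germ-cell transmission or systemic toxicity in animals. It describes no embryo-fetal study, so the question is open rather than answered either way. The other inference is that the efficacy result is compromised. Nothing in the gap touches the primary comparison, the sample size or alpha.

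**Conclusion.** The inconsistency holds and should be corrected. Inclusion 9 calls for agreement to repeat tests; the protocol and the SAP schedule none after screening. The only test can be up to 60, 77, 91 and 105 days old at injections 1 to 4, or 30, 47, 61 and 75 days under the SAP's screening column. These are maxima: they assume a test on the first day of the window and the latest permitted injection visit. The number of women exposed to the gap is unknown and may be zero, and contraception makes an undetected pregnancy less likely. This is an internal inconsistency in a safety procedure, worth an amendment because the remedy is cheap and the protocol already foresees it.

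**What to change.** For women of child-bearing potential in all three arms, at the same visits so that the blind is kept:

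1. Add a urine pregnancy test to the pre-injection lists 3.4.6.1, 3.4.7.1, 3.4.8.1 and 3.4.9.1, and require a negative result before injecting. Those lists cover the 4 hours before injection, so the test would be at most 4 hours old.
2. Tick the four pre-dose columns of the pregnancy-test row in Appendix 1 and SAP Table 2, and move 4.1.7 from section 4.1 to 4.2.
3. State what follows a positive result, separately for Day 0 and later visits. One rule for all four would conflict with the protocol's own categories.
   - *Day 0, before any dose:* do not treat. She no longer meets the entry criteria, so handle her as a screen failure and replace her under 3.4.3.1 and 6.3. If already randomized she stays in the SAP's ITT population; undosed, she is outside the Safety population.
   - *Day 14, 28 or 42:* withhold further injections and continue safety follow-up in the study. Word this as stopping treatment and not as leaving the study, so that the rule in 3.5.2, "Discontinued patient(s) will be replaced in any treatment arm if discontinuation occurs prior to the 90 Day follow-up", is not triggered.

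Inclusion 9 leaves the timing open. The injection visits are proposed because they already take place and are when the drug is given. Deleting the repeat-test phrase would also remove the contradiction, but would give up the safeguard.

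Cost: four urine tests per woman at existing visits. With an illustrative 0 to 5 such women (an assumption, not a figure from the documents), that is 4 × 0 = 0 to 4 × 5 = 20 tests, plus amendment wording. The one analytic side effect is that a subject with a withheld dose may not count as correctly dosed and may leave the per-protocol population, on which the primary efficacy analysis is run. At planned sizes, one such subject is 1/20 = 5% of an active arm or 1/10 = 10% of placebo. She remains in the ITT population.
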